## Variables

The investigators will look at several variables and adjust for these where needed. The variables obtained from DHR is body mass index (BMI), age, gender, time of surgery, diagnosis, type of prosthesis and fixation method, whether cement is used and if it contains antibiotics, previous operations on the same hip and ASA score. ASA score and BMI are only available from 2017 and onwards in DHR.

From NPR, concomitant diagnoses will be obtained to produce an Elixhauser comorbidity score, and socioeconomic factors, such as income and education will be obtained from the Danish Income Statistics Register and Education Register.

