## Methods

The data is reported according to the RECORD guidelines (45) and is stored in the servers of Statistics Denmark, where the data will be analyzed.

Study population:

All people  $\geq 18$  years receiving a primary total hip arthroplasty in Denmark between 01.01.2010-31.12.2020 registered in DHR are included. Patients receiving a THA due to a hip tumor or metastasis are excluded, as well as patients with erroneous registration in DHR.

Exposure:

Surgery performed in an OR with LAF compared with surgery in an OR with TAF.

Follow-up:

Follow-up starts on the operation day and ends 365 days postoperatively. Follow-up is also ended at time of any revision, death or emigration.

Null hypothesis:

There is no difference in the risk of PJIs after a THA performed in a LAF OR as opposed to in a TAF OR.

Alternative hypothesis:

There is a lower or higher risk of PJIs after a THA performed in a LAF OR as opposed to in a TAF OR.

Endpoints:

*Primary endpoint:*

Revision due to infection, measured at t=90 days and t=365 days. Revision is defined as the first surgical intervention in the same hip after a primary THA with debridement, replacement, or removal of prosthetic parts.

A follow-up time of 90 and 365 days respectively is chosen, since 90 days is the recommended surveillance period in the United States and is traditionally the limit between early and late infections, whereas it is important to have a follow up of a year not to miss up to 20 % of the infections (46,47). At 1 year, 80-90 % of the surgically requiring infections that will occur in the lifetime of the hip prosthesis have taken place. After 1 year, the infection rate drastically decreases and is less likely to be due to contamination during surgery (30,47).

PJI is considered present when at least one of the following two criteria exists.

1. Two or more intraoperative deep-tissue samples of the same bacteria, isolated from at least three deep-tissue samples.
2. Deep infection is reported to DHR by the surgeon upon revision surgery.

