#### Statistical analysis:

Descriptive results for continuous variables will be shown as mean(SD)/median(range) depending on the distribution of the variables. Categorical variables will be presented using frequencies and percentages. Persons operated in LAF and TAF ORs are compared using t-tests/Wilcoxon-tests and chi-square tests, respectively. This is supplemented with cumulative incidence plots showing risk of infection (primary outcome) for LAF and TAF, regarding revision due to other causes and death as competing events. The two groups are compared using Grays test. To fulfill the requirements at Statistics Denmark about data on individual persons, a smooth curve is used to make the plot rather than the statistical correct step-function. Information at time 90 and 365 days after the operation will be presented. This type of plot will be used for all endpoints.

For the primary endpoint, two Cox regression analyses will be performed with the time to PJI as outcome. One model will only cover the first 90 days of follow-up, the other will cover all 365 days of follow-up. Censoring is made at time of revision due to other causes than PJI, death, emigration, and end of follow-up (365 days after operation), whichever comes first. Bilateral THA will be included in the model as two observations with inclusion of a time-dependent variable conditioning on the status of the other hip (53). A robust sandwich covariance matrix estimate is used to account for the intrapersonal dependence.

The model will include the following potential confounders:

Education, age, comorbidities, gender, previous hip surgery, primary diagnosis, type of cement, type of fixation, year of surgery, income and duration of surgery. ASA and BMI will be adjusted for in sensitivity analysis c). A direct acyclic graph is used when determining the variables needed to adjust for.

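### Duration of surgery is known only after the LAF or TAF room is in use, yet no planned adjusted HR leaves it out: pre-specify the Cox models with and without it

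*Combined protocol and SAP*

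**What the plan says.** The Methods section defines the exposure as "Surgery performed in an OR with LAF compared with surgery in an OR with TAF", and time zero as the day of surgery: "Follow-up starts on the operation day and ends 365 days postoperatively".

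Under Statistical analysis, "For the primary endpoint, two Cox regression analyses will be performed with the time to PJI as outcome", one model for 90 days and one for 365 days. The covariates are introduced with "The model will include the following potential confounders", and the list ends with "year of surgery, income and duration of surgery". The only reason given for the choice is: "A direct acyclic graph is used when determining the variables needed to adjust for". No graph is reproduced, and the text does not say what role duration plays in it.

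Similar Cox models are planned for both secondary endpoints and for the sensitivity analyses. Sensitivity analyses a) and b) change the outcome definition. Analysis c) restricts the period to 2017-2020 and adds BMI and ASA. None is said to drop duration.

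The Variables section lists, from the hip register, "body mass index (BMI), age, gender, time of surgery, diagnosis, type of prosthesis and fixation method". Duration of surgery is not named there.

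**The concern.** A confounder is a common cause of exposure and outcome, or a stand-in for one. Realised operating time cannot itself have caused the choice of room, because it is not known until the operation is over. It can only stand in for something earlier, such as expected complexity or the team, or be a consequence of what happened in the room. These cases call for different handling:

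- If duration stands in for a common cause of room choice and PJI, adjusting for it removes some confounding.
- If the room or its set-up changes operating time, and time affects PJI, adjusting removes part of the effect being estimated.
- If the room changes operating time, and unmeasured factors (surgeon skill, intraoperative problems) drive both time and PJI, adjusting opens a non-causal path.

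The Abstract and Perspectives sections say the study should help decide which ventilation to install when hospitals are built or renovated. That decision turns on the total effect of LAF versus TAF. With duration in every adjusted model, a reader could not tell whether the reported HR depends on this covariate.

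**Working it through.** The documents give no sample size, event count, effect size or figure on duration, so there is no plan figure to reproduce. The check is one of timing, followed by an illustration in which every duration input is assumed.

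**1. Order in time.** Room (exposure), then operation, then duration known, then follow-up for PJI. Duration is therefore a post-exposure quantity in both primary models.

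**2. Which planned outputs omit duration?** Only the cumulative incidence plots with Gray's test, which are unadjusted. No HR adjusted for the other covariates but not for duration is planned.

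**3. Route through operating time.** Assume a room-related mean difference of d minutes (LAF longer) and a hazard ratio h per 10 minutes. For a rare event, total HR / duration-adjusted HR = h^(d/10).

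| d (min) | h = 1.05 | h = 1.10 | h = 1.20 |
|---|---|---|---|
| 0 | 1.000 | 1.000 | 1.000 |
| 2 | 1.010 | 1.019 | 1.037 |
| 5 | 1.025 | 1.049 | 1.095 |
| 10 | 1.050 | 1.100 | 1.200 |

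If LAF shortens surgery, the reciprocals apply: 0.976 to 0.913 at 5 minutes, 0.952 to 0.833 at 10.

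Simulation check: Poisson log-link models, 2,000,000 hips per scenario, baseline risk 0.8 % (the upper end of the registered first-year incidence in Rationale and background), duration SD 20 minutes, direct RR 0.85, h = 1.10. Total versus adjusted RR was 0.843 vs 0.843 at 0 minutes, 0.890 vs 0.846 at 5, and 0.942 vs 0.858 at 10. The ratios 0.890/0.846 = 1.052 and 0.942/0.858 = 1.098 agree with 1.049 and 1.100.

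**4. Route through an unmeasured shared cause.** Assume no effect of room or duration on PJI. An unmeasured factor, unrelated to room, adds 10 minutes per SD and multiplies PJI risk by 1.5 per SD. Duration SD within room is 20 minutes (variance 400). Given duration, a LAF hip has a value of the factor lower by (10/400) × d SD, so adjusted RR = exp(−ln 1.5 × 10d/400):

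- d = 0: 1.000
- d = 2: 0.980
- d = 5: 0.951
- d = 10: 0.904

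The true value is 1.00 throughout. If LAF shortens surgery, the reciprocals apply (1/0.904 = 1.11 at 10 minutes). In simulation, adjusted over unadjusted RR was 1.007/1.007 = 1.000, 0.967/0.986 = 0.981, 0.954/1.005 = 0.949 and 0.924/1.022 = 0.904 (SE of each adjusted log RR about 0.015).

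**5. Yardstick.** With E events and equal groups, an HR below 1 reaches two-sided 0.05 at about exp(−1.96 × 2/√E). For an assumed 640 and 1,120 events this is 0.856 and 0.889. With an assumed 80/20 split, exp(−1.96/√(0.16E)) gives 0.824 and 0.864. A null total effect shifted by the route in step 3 with h of 1.05 to 1.10 appears no lower than 1/1.10 = 0.909, short of all four. Only the corner case h = 1.20 with d = 10 (1/1.20 = 0.833) passes some of them.

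**The case against.** Four points can be made for leaving the plan as it is.

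- *Nothing in the documents links ventilation to operating time.* LAF is described as acting through airborne bacteria. This stands. Both routes need the room to change duration, and both give exactly 1.00 when d = 0.
- *Duration may be worth adjusting for.* Surgeon, team and hospital are not in the covariate list, BMI and ASA enter only in sensitivity analysis c), and a hospital may come with its type of room. If such factors drive both operating time and PJI, duration captures part of that confounding. This also stands, and it makes outright removal a trade-off of unknown size.
- *A graph is used to choose the variables.* A reader might infer that adjusting for duration contradicts that graph. The documents do not support this, because the graph is not shown. All that can be said is that duration's role is unexplained. Nor does the sentence settle the matter, since the list is already worded as what the model will contain.
- *Some of this is already covered.* The planned LAF/TAF comparison of continuous variables would probably include duration, and the cumulative incidence curves do not condition on it. Neither is a substitute for an otherwise adjusted HR without duration.

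The wording in Variables, "age, gender, time of surgery, diagnosis, type of prosthesis and fixation method", could mean the date or the length of the operation. That is a query about definition and is no evidence of bias.

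**Conclusion.** The point holds as a cheap improvement. A post-exposure quantity is in the primary adjustment set, its role is not explained, and no planned adjusted HR shows what happens without it.

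A reader might go further and infer that the primary HR is biased, or biased in a known direction. The documents do not support that. They give no evidence that ventilation affects duration, and the shift could go either way. A stronger shared cause would give larger shifts: an assumed HR of 1.32 per 10 minutes with d = 5 turns a null into 1.32^(−0.5) = 0.87. If that factor adds 15 minutes per SD and doubles PJI risk, it must explain about 60 % of the variance in duration (implied variance ln 2 × 15 / (ln 1.32 / 10) ≈ 374; 15²/374 ≈ 0.60). That is an extreme case and should not be read as an expected size.

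For moderate assumptions (5 to 10 minutes, HR 1.05 to 1.10 per 10 minutes), the total and adjusted HR differ by about 2 to 10 %. That would not by itself turn a null into a significant result under the assumed event counts. It could matter when the true difference is small, or when the estimate lies near the boundary.

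**What to change.** In the Statistical analysis section:

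1. Pre-specify the 90-day and 365-day Cox models, and the similar models for the secondary endpoints, both with and without duration of surgery, all other covariates unchanged.
2. Name in advance which version is primary. If the target is the total effect of choosing a ventilation system, as the stated use in hospital design suggests, the model without duration is the natural primary one, with the duration-adjusted HR beside it.
3. Show the graph, or state in a sentence whether duration is treated as a stand-in for complexity or team, as an intermediate, or as both.
4. Report duration by LAF/TAF. If it hardly differs, the concern falls away. If it does differ, a gap between the two HRs may be confounding removed or bias added, and should be discussed as such.
5. In Variables, give the source and definition of duration, and say what the listed time of surgery means.

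The cost is SAP wording and one extra fit per model. The downsides are two HRs to report per endpoint, and that the model without duration gives up a proxy for case complexity. Fixing the choice before results are seen also avoids choosing between the two afterwards.

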### Missingness

Thanks to the Danish registers, there is no loss to follow-up for the primary and secondary endpoints, nor for the endpoints of the sensitivity analyses. Information for most of the confounders is based on mandatory registration in DHR, thus it is expected a very limited amount of missing data in the confounders (less than 5 % with missing information about one/several confounders). The missingness is not likely to be associated with the exposure, thus the complete case analysis is expected to be valid (55).

If the missingness is found to be more pronounced, multiple imputation will be used to create a full analysis data set. The imputation will use 100 samples. Multiple imputation will be made using R (The R Foundation). Results from analysis on the full analysis data set as well as for the complete case analysis will be presented.

### Ethical aspects

The study is registered in Pactius, Region Hovedstaden. The study is approved by the Danish Health Data Authority. Since it is an observational study, an approval by an ethical committee is not needed. An approval from the Danish Society for Patient Safety is not needed since this study solely uses anonymized data from registers and not from medical records. The protocol is uploaded to clinicaltrials.org to maximize transparency of the research process.

## Perspectives

When constructing or renovating a hospital, it is crucial to choose a ventilation system that minimizes PJIs, while being cost-efficient. Previous studies on LAF vs TAF are based on data from national registers. Since registration of PJI is reported immediately to DHR and other registers after surgery, the microbiology results are not taken into consideration when the revision cause is reported. This study is novel, because it gives a more accurate picture of the PJI incidence and can be part in guiding the decisions when renovating or designing new hospitals, in order to decrease the risk of PJI.

## Appendix A

List of antibiotics screened for 2 weeks after revision, originating from the study by Lidgren et al. from 2014 (56), adapted to Danish conditions

J01CA04 Amoxicillin  
J01CR02 Amoxicillin and clavulanic acid  
J01CE02 Phenoxymethylpenicillin  
J01CF05 Flucloxacillin  
J01CF01 Dicloxacillin  
J01FA01 Erythromycin  
J01FA06 Roxithromycin  
J01FA09 Clarithromycin  
J01FA10 Azithromycin  
J01XC01 Fucidin  
J04AB02 Rifampicin  
J01FF01 Clindamycin  
J01XX08 Linezolid  
J01XD01 Metronidazole  
J01MA02 Ciprofloxacin  
J01MA12 Levofloxacin  
J01MA14 Moxifloxacin  
J01EE01 Sulfametoxazol and trimetoprim
